9.3 Analysis of other pharmacokinetic variables

The other PK variables and their analysis are the followings:

- Inter- and intra-study participant coefficients of variation (variability) in PK parameters C_{max} , $AUC_{(0-12)}$, $C_{max,ss}$, and AUC_{τ} for PSL and its metabolites

Inter-study subject and intra-study subject variability on the PK parameters for PSL and its metabolites will be estimated from the mixed effects analysis described in [Section 9.1](#). The point estimate (CV%) and 2-sided 90% CI for the inter-subject variability will be derived from the subject effect of the variance covariance matrix, and for the intra-subject variability, the point estimate (CV%) and 2-sided 90% CI will be derived from the residual effect of the variance-covariance matrix.

- Pharmacokinetic parameters C_{max} , $AUC_{(0-12)}$, $C_{max,ss}$, and AUC_{τ} (and profile) data derived from MITRA dried blood concentration for PSL and its metabolite (only [REDACTED])
- The blood concentrations and blood PK variables for PSL and its metabolite based on the MITRA microsampling will be summarised and plotted as described in [Section 9.1](#).
- As exploratory analysis, point estimates for the ratio of geometric means for the PK parameters C_{max} , $AUC_{(0-12)}$, $C_{max,ss}$, and AUC_{τ} for PSL based on the MITRA dried blood microsampling compared to the plasma conventional venous sampling along with the 2 sided 90% CIs will be computed using the least squares means and the root mean squares of error from a specific linear mixed effects model, based on of the log-transformed data with subsequent exponential transformation for the following periods:
 - Overall: conventional venous compared to MITRA
 - Period 1: conventional venous compared to MITRA
 - Period 2: conventional venous compared to MITRA
 - Period 3b: conventional venous compared to MITRA
- Scatter plots of the MITRA dried blood concentrations versus venous plasma concentrations for PSL and its metabolite will be presented. Furthermore a linear regression plot of the MITRA dried blood concentrations and venous plasma concentrations for PSL and its metabolite including the regression lines for the mean along with 90% confidence intervals will be presented for the log data.
- The predose trough concentrations for both plasma conventional venous and MITRA dried blood sampling methods obtained the Days 2 to 4, 13 to 15, and 27 to 33 will be listed separately. The trough PSL concentrations will be summarized by treatment period and day. Geometric mean along with their 95% CI for the trough concentrations will be plotted against time, with the 3 treatment periods overlaid in one figure (one plot for each sampling method).
- Erythromycin plasma concentrations may be listed if blood samples are bioanalyzed for erythromycin assessment.

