#### 3.3 Exploratory objectives

The exploratory objectives of this study are to:

- Estimate the inter- and intra-study participant variability in the plasma PK of PSL and its metabolites following administration of PSL in the presence and absence of erythromycin
- Evaluate and compare the venous blood and MITRA microsampling (dried blood) PK of PSL and its metabolite [REDACTED] following administration of PSL in the presence and absence of erythromycin
- Archive blood samples for genotyping of drug metabolizing enzymes and biomarkers

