### **5.3.2 Microsamples of capillary blood**

Samples from a finger skin prick will also be collected using the MITRA device at each of the time points identified for the venous blood samples in [Section 5.3.1](#).

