### **9.5 Bioanalytical method**

Plasma concentration of PSL and metabolites will be determined with a validated bioanalytical method. Plasma and blood concentration of parent PSL collected by MITRA devices respectively will be determined with a scientific validated bioanalytical method.

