3.9 Changes to protocol-defined analyses

The protocol states that MITRA dried blood microsampling method will be compared to those of the plasma conventional venous sampling method using descriptive analysis (tables with summary statistics and graphs). Nonetheless, as described in [Section 9.3](#), the exploratory analysis will also be described using linear mixed effects model.

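### The exploratory MITRA-to-plasma ratio in SAP 9.3 cannot by itself show whether the sampling methods agree, and no confidence interval is planned for whether MITRA reproduces the erythromycin effect

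*SAP*

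**What the plan says.** **Objective.** Protocol 3.3 lists, among the exploratory objectives: "Evaluate and compare the venous blood and MITRA microsampling (dried blood) PK of PSL and its metabolite", and sets that comparison in the presence and absence of erythromycin. Protocol 12.3.1 makes the method comparison descriptive (summary tables and graphs).

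**Matrices.** Protocol 5.3.2: "Samples from a finger skin prick will also be collected using the MITRA device at each of the time points" used for venous sampling. Protocol 9.5: "Plasma and blood concentration of parent PSL collected by MITRA devices respectively will be determined". SAP 9.3 likewise refers to blood for MITRA and plasma for the conventional method. The objective's reference to venous blood therefore describes the sampling route; the conventional assay is on plasma.

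**Analysis.** SAP 3.9 declares one change from the protocol: "the exploratory analysis will also be described using linear mixed effects model". SAP 9.3 gives the content, which opens: "As exploratory analysis, point estimates for the ratio of geometric means for the PK parameters". Those parameters are AUC(0-12), AUCtau, Cmax and Cmax,ss, and the comparison is worded as "for PSL based on the MITRA dried blood microsampling compared to the plasma conventional venous sampling along with the 2 sided 90% CIs". These are to be given overall and for Periods 1, 2 and 3b. The lead sentence puts MITRA over plasma; each of the four items below it puts conventional over MITRA.

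**Erythromycin effect.** The model comparing Period 3b with Periods 1 and 2 is specified for plasma PSL (SAP 9.1) and plasma metabolites (SAP 9.2). For MITRA, SAP 9.3 says only: "The blood concentrations and blood PK variables for PSL and its metabolite based on the MITRA microsampling will be summarised and plotted" in the manner of Section 9.1. Scatter plots and a log-scale regression of MITRA on plasma concentrations are also planned.

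**Not stated.** Neither document gives a PSL blood-to-plasma ratio, a conversion between matrices, a reference value, agreement limits or a rule for reading the ratio. Hematocrit is measured (Protocol Table 10-1) but not linked to this analysis, and SAP 4.1 plans no covariate adjustment.

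**The concern.** A ratio of two sampling methods with a confidence interval invites reading as a measure of agreement. Here the two methods also measure different matrices. A device that recovers all the drug in the blood it takes up would still give a ratio away from 1 if PSL is distributed unequally between red cells and plasma. Conversely, a device that loses drug could give a ratio near 1 if partition into red cells offset the loss. The planned ratio cannot separate these cases.

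In an interaction study the more useful question is whether MITRA gives the same erythromycin effect as plasma, and the objective's wording points to it. A partition factor that is constant across periods drops out of that comparison, but no model-based estimate or interval is planned for it.

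What is at stake is the value of the finger-prick sampling, which is done at every venous time point: the exploratory objective it serves could end without an interpretable answer. The two stated directions also leave the programmer unable to tell which ratio to report.

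**Working it through.** **Plan's own figure.** The documents give no figure for the MITRA comparison. The only sample size is for the primary AUCtau ratio: SD of the difference = 1.4 × √(2 × (1 − 0.5)) = 1.4, half-width 0.75, two-sided alpha 0.05, 80% probability of achieving that half-width. This reproduces n = 20, which is used below only as the number of completers.

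**1. What the ratio estimates.** Let d = log(MITRA) − log(plasma) for one participant in one period. Then

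mean d = log(B) + log(C) + log(F),

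where B is blood-to-plasma partition, C the capillary-venous difference and F device and assay recovery. exp(mean d) equals 1 for a perfect device (C = F = 1) only if B = 1.

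B can be written as 1 − H(1 − K), with H the hematocrit and K the red-cell-to-plasma concentration ratio. Over an assumed H of 0.36 to 0.50, B is 0.64 to 0.50 at K = 0, 0.82 to 0.75 at K = 0.5, and 1.00 at K = 1. The documents give no K for PSL.

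**2. How often a perfect device's 90% CI would exclude 1.** Assumed: n = 20 pairs in one period, independent errors, equal CV for each method.

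- SD of d = √2 × √ln(1 + CV²). At CV 20%: √2 × 0.198 = 0.280.
- SE = 0.280/√20 = 0.0626.
- At B = 0.8: noncentrality = ln(0.8)/0.0626 = −3.56. With t(0.95; 19) = 1.729, the noncentral t probability is 96%.

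| Assumed B | CV 10% | CV 20% | CV 30% |
|---|---|---|---|
| 0.6 | 100% | 100% | 100% |
| 0.7 | 100% | 100% | 98% |
| 0.8 | 100% | 96% | 75% |
| 0.9 | 94% | 49% | 29% |
| 0.95 | 47% | 20% | 15% |
| 1.0 | 10% | 10% | 10% |
| 1.1 | 90% | 43% | 26% |
| 1.25 | 100% | 96% | 75% |

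Pooling three periods as about 60 independent pairs at CV 20% gives 89% at B = 0.9, 41% at 0.95 and 10% at 1.0. The result therefore runs from the nominal 10% to near certainty, depending on an input the documents do not supply.

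**3. The masked case.** Recovery 0.75 with partition 1.33 gives 0.75 × 1.33 = 0.9975, a ratio of about 1 from a device that loses a quarter of the drug.

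**4. The contrast not planned.** For each participant,

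D = d(3b) − [d(1) + d(2)]/2.

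exp(mean D) is the MITRA erythromycin ratio divided by the plasma erythromycin ratio. A constant log(B) cancels: log(B) − [log(B) + log(B)]/2 = 0.

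Var(D) = SD² × (1 + 1/4 + 1/4) = 1.5 SD², so SE = SD × √(1.5/20). For an assumed within-participant SD of d of 0.15 to 0.30:

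- SD 0.15: SE = 0.041; 1.729 × 0.041 = 0.071; 90% CI factor exp(0.071) = 1.07.
- SD 0.30: SE = 0.082; 1.729 × 0.082 = 0.142; 90% CI factor exp(0.142) = 1.15.

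By the same noncentral t calculation, a MITRA loss of 20% confined to Period 3b would give a 90% CI excluding 1 with probability above 99% at SD 0.15 and 83% at SD 0.30.

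**5. What the planned output allows.** The point estimate of exp(mean D) can be back-calculated, given complete data, as the Period 3b ratio divided by the geometric mean of the Period 1 and Period 2 ratios. Its paired CI cannot: that needs the within-participant variance of D, or the covariances between the period ratios, and neither is a planned output.

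**The case against.** The strongest reply is that the plan makes no claim of agreement. A reader might infer that the ratio is to be judged against 1, and hence that a sound device would almost always appear to disagree with plasma. The documents do not support this. Protocol 12.3.1, SAP 3.9 and SAP 9.3 name no reference value, limit or decision rule, and the frequency depends on the unstated blood-to-plasma ratio. At 20% CV and n = 20, exclusion of 1 is 49% or less for ratios from 0.9 to 1.1. This part of the reply stands. What remains is that the SAP does not say how the ratio should be read.

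Nor does the ratio measure partition alone. It is a product of three factors, and an overall MITRA-to-plasma factor is a legitimate descriptive result. The SAP already calls the matrices dried blood and plasma, and in the log-scale regression a constant partition factor would appear as an intercept shift. These points stand too, and they are why the ratios should be kept.

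It would also be too strong to say that the erythromycin effect by MITRA is left without any estimate. Geometric means with 95% CIs by period are planned, and the contrast's point estimate can be back-calculated. Only the model-based estimate and the paired CI are missing.

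Finally, the proposed contrast has its own blind spot. It cannot see a proportional MITRA bias that is equal in all periods, so the masked case in step 3 would pass it. It also assumes that partition stays constant while exposure rises about threefold (the protocol's sample size assumes a ratio of 3.2). This stands, and is the reason to add the contrast beside the ratios rather than in place of them.

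**Conclusion.** The point holds as a minor recommendation on an exploratory analysis. Three things follow from the documents without assumption: the ratio sets dried capillary blood against venous plasma with no conversion or rule for interpretation; its direction is stated both ways within SAP 9.3; and the with/without-erythromycin model is not applied to MITRA, although Protocol 3.3 sets the comparison in the presence and absence of erythromycin.

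The size of any departure from 1 is not determinable from the documents; the exclusion probabilities rest on assumed blood-to-plasma ratios and CVs. That a constant partition factor cancels from the contrast is algebra and does not depend on PSL's value. The contrast's 90% CI factor of 1.07 to 1.15 assumes 20 completers with all three periods and a within-participant SD of the log difference of 0.15 to 0.30.

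The primary plasma comparison is unaffected.

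**What to change.** In SAP 9.3:

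1. Apply the Section 9.1 with/without-erythromycin model to the MITRA Cmax, AUC(0-12), Cmax,ss and AUCtau. Beside the existing ratios, add the method-by-treatment contrast: the MITRA ratio of Period 3b to Periods 1 and 2, divided by the corresponding plasma ratio, with its 90% CI taken from within-participant log differences.
2. Report the overall and per-period ratios in one direction (MITRA/plasma), label them dried blood-to-plasma ratios, and state that 1 is not necessarily the value expected under agreement.
3. State the contrast's limits: it cannot detect a proportional bias common to all periods, and it assumes constant partition across exposures. The absolute ratios therefore stay beside it.

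The cost is SAP wording, the Section 9.1 model run on the MITRA parameters and one added contrast, all on data already collected. No new samples, assays or participants are needed.

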### **5.3.1 Venous blood**

Venous blood samples for PK analysis will be performed as follows:

- Predose and 0.25h, 0.5h, 0.75h, 1h, 1.25h, 1.5h, 2h, 3h, 4h, 6h, 8h, and 12h post first dose of PSL during each Treatment Period (Day 1, Day 12, and Day 26)
- Predose and 0.25h, 0.5h, 0.75h, 1h, 1.25h, 1.5h, 2h, 3h, 4h, 6h, 8h, 12h, 24h, 36h, 48h, and 72h post last dose of PSL during Treatment Period 1 (Day 5) and Treatment Period 2 (Day 16)

- Predose and 0.25h, 0.5h, 0.75h, 1h, 1.25h, 1.5h, 2h, 3h, 4h, 6h, 8h, 12h, 24h, 36h, 48h, 60h, 72h, 96h, and 120h post last dose of PSL during Treatment Period 3b (on the morning of Day 33)

Additional PK trough samples will be taken immediately prior to each morning dose of PSL during Treatment Period 1 (Day 2 through Day 4) and Treatment Period 2 (Day 13 through Day 15) and each morning combination dose during Treatment Period 3b (Day 27 through Day 33).

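### The MITRA-versus-plasma regression names no participant effect; fitted as an ordinary regression to up to 105 serial pairs per person, its 90% band is too narrow wherever residuals correlate within participant

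*SAP*

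**What the plan says.** SAP 9.3 plans scatter plots of the two sampling methods against each other, for PSL and one metabolite. It adds a linear regression of the paired values, and the figure "including the regression lines for the mean along with 90% confidence intervals will be presented for the log data". It does not state a participant effect, a covariance structure, a unit of analysis, or whether the periods are pooled in one fit.

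The SAP does name such structure nearby. The primary PK comparison in SAP 9.1 has a random subject effect. In SAP 9.3 the MITRA-to-venous ratios of Cmax, AUC(0-12), Cmax,ss and AUCτ come from a linear mixed effects model. SAP 3.9 records that mixed model as an addition to the descriptive comparison in Protocol 12.3.1.

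The pairing is set in Protocol 5.3.2: finger-prick samples are taken with the "MITRA device at each of the time points identified for the venous blood samples". Protocol 5.3.1 gives those time points, for example "Predose and 0.25h, 0.5h, 0.75h, 1h, 1.25h, 1.5h, 2h, 3h, 4h, 6h, 8h, and 12h post first dose of PSL during each Treatment Period" on Days 1, 12 and 26. SAP 9.3 lists trough concentrations for both sampling methods, which confirms that troughs are paired too. Protocol 12.7 and SAP 2.4 plan 20 completers from up to 28 participants.

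**The concern.** Dried blood and plasma are different matrices, so one participant's blood-to-plasma relationship may sit consistently above or below the average line. The pairs from that participant then share an error. An ordinary regression counts every pair as separate evidence, and its confidence band reflects the number of pairs more than the number of people.

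The band is labelled as a 90% confidence interval for the mean line. If it is computed in this way, a reader comparing the two sampling methods will see more precision than the study has. What is at stake is the interpretation of one exploratory plot.

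**Working it through.** The documents give no pair count, residual correlation or band width for this plot, so there is no stated figure to reproduce.

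**1. Scheduled pairs per participant** (Protocol 5.3.1 and 5.3.2)

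- First-dose profile (Days 1, 12, 26): predose + 12 postdose = 13 each.
- Last-dose profile, Days 5 and 16: 13 + 4 (24, 36, 48, 72h) = 17 each.
- Last-dose profile, Day 33: 13 + 7 (24, 36, 48, 60, 72, 96, 120h) = 20.
- Troughs: 3 in Period 1, 3 in Period 2, and 6 in Period 3b. The Day 33 trough coincides with that day's predose sample and is not counted again.

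Period 1 = 13 + 17 + 3 = 33. Period 2 = 33. Period 3b = 13 + 6 + 20 = 39. Total = 105 per participant, or 20 × 105 = 2,100 for 20 completers. This is a maximum. SAP 4.2.1 treats values below the quantification limit as missing in individual concentration figures, and the Day 1 predose sample precedes any PSL.

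**2. Narrowing at the centre of the line**

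Let m be the pairs per participant and ICC the within-participant correlation of the regression residuals. The true variance at the centre is the ordinary one multiplied by 1 + (m − 1) × ICC, so the ordinary band is too narrow by

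factor = √(1 + (m − 1) × ICC).

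For m = 105: √(1 + 104 × 0.01) = √2.04 = 1.4; √(1 + 104 × 0.05) = √6.2 = 2.5; √(1 + 104 × 0.30) = √32.2 = 5.7.

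| ICC (assumed) | m = 105 | m = 60 (heavy losses) | m = 33 (one period) |
|---|---|---|---|
| 0 | 1.0 | 1.0 | 1.0 |
| 0.01 | 1.4 | 1.3 | 1.1 |
| 0.05 | 2.5 | 2.0 | 1.6 |
| 0.30 | 5.7 | 4.3 | 3.3 |

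With m = 33 and ICC 0.06: √(1 + 32 × 0.06) = √2.92 = 1.7. With m = 105, a factor of 3 needs ICC = (9 − 1)/104 = 0.08.

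**3. Approximate coverage at the centre**

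Coverage of a nominal 90% interval is about 2Φ(1.645/factor) − 1. For m = 105 this gives about 75% at ICC 0.01, 49% at 0.05 and 23% at 0.30.

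**4. Check on an actual regression**

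Ordinary least squares was simulated on log-log data with 20 participants, 92 pairs each (some late samples lost) and 500 datasets per setting. The entries are the true standard deviation of the estimate divided by its ordinary standard error. Participants differ by a constant offset only.

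| ICC | Centre of line | Slope |
|---|---|---|
| 0 | 1.0 | 1.0 |
| 0.05 | 2.3 | 1.9 |
| 0.10 | 3.1 | 2.2 |
| 0.30 | 5.4 | 3.6 |

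The centre agrees with the formula at m = 92 (for example √(1 + 91 × 0.30) = 5.3). With half the between-participant spread in log concentration, the slope factor falls to 1.3 at ICC 0.05 and 2.5 at 0.30. If slopes also vary between participants, the slope is no longer protected: a slope SD of 0.05 with no offset gave about 2 at the centre and 4 for the slope.

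**The case against.** The strongest reply is that the SAP never says the pairs are independent. It uses mixed models for its formal PK comparisons, so this regression may simply be under-described. That is fair as a reading of the text: the independence assumption is inferred from silence. But a linear regression with a confidence band and no further terms is most naturally programmed as ordinary least squares, and the mixed models elsewhere in the SAP show that participant structure was written down where it was intended.

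The second reply is about size. A reader might infer that the band is several times too narrow. The documents do not support that as a general statement. They give no ICC, and the factor is 1.0 at ICC 0 and reaches 3 only at about 0.08 with all 105 pairs. Losses below the quantification limit reduce the pairs. SAP 9.3 speaks of lines in the plural, which may mean one per period or one per analyte. By period there are only 33, 33 and 39 pairs. The formula also describes the centre of the line, not the whole band. All of this stands.

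A reader might also infer that 2,100 pairs carry only about 20 independent pieces of information. That is the limit as ICC approaches 1. Dividing 2,100 by 6.2 and by 32.2 gives effective sizes of about 339 at ICC 0.05 and 65 at ICC 0.30.

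Lastly, a reader might suppose that the plot decides whether dried blood can stand in for plasma. The objective in Protocol 3.3 is to evaluate and compare the two methods. No agreement criterion is tied to the plot, and the intervals for the parameter ratios come from the separate mixed model.

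**Conclusion.** The point holds in a limited form. SAP 9.3 attaches a 90% confidence band to a regression on repeated pairs and names nothing to account for the repetition. Fitted as an ordinary regression, the band is too narrow for any positive within-participant residual correlation. At the centre of the line with 105 pairs the factor is about 1.4, 2.5 and 5.7 at ICCs of 0.01, 0.05 and 0.30.

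These ICCs are assumptions. The figures also assume that all scheduled pairs are usable and enter one pooled fit; fewer pairs or by-period lines make the effect smaller. The slope is less affected if participants differ only by a constant offset. The consequence is minor: this is an exploratory plot without a decision rule, and neither the primary comparison nor the MITRA-to-venous parameter ratios depend on it.

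**What to change.** In SAP 9.3, state that the log-log regression is fitted with participant as a random effect (intercept and, if estimable, slope), or with participant-clustered standard errors, and that the 90% band is drawn from that fit. State in the same place whether lines are fitted overall or by period, and how pairs with a value below the quantification limit are treated. If no such model is wanted, present the line without a confidence band.

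The cost is a short change to the SAP wording and one changed model. The band becomes wider. Data collection and the primary analysis do not change.

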10 SAFETY ANALYSES

All safety summaries and listings will be performed using the FAS. Unless stated otherwise, all summaries including figures will be by treatment period (Period 1 and Period 2 pooled, Period 3b, Period 3a and Period 3c pooled and EOS/SFU) as detailed in [Table 13.1](#). Summaries for continuous variables by timepoint will be based on the averaged value across the pooled periods. Categorical variables will be summarized according to the actual period (no pooling).

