3.3 Definition of Baseline values

In general, Baseline will be the last non-missing value prior to dosing. Scheduled or unscheduled measurements can be used as the Baseline value.

Measurement-specific Baseline timepoints are presented in [Table 3–1](#).

Table 3–1: Definition of Baseline

Measurement	Definition of Baseline

 Hematology, serum chemistry, urinalysis 	Baseline or if missing the Screening value

 Vital signs 	
Pre-dose for each treatment period.
 
Treatment Period 1 pre-dose Day 1 or if missing Day -1. If Day -1 is missing the Screening value will be used.
 
Treatment Period 2 pre-dose Day 12 or if missing pre-dose Day 1
 
Treatment Period 3 pre-dose Day 23 or if missing pre-dose Treatment Period 1 value
 
Otherwise baseline = day -1 pre-dose

Measurement	Definition of Baseline

 ECG 	
Time-matched predose for each treatment period.
 
Treatment Period 1 Day-1 Morning: predose, 1h, 2h, 3h, 6h similar “postdose” ; Evening: 0.5h “postdose”
 
Treatment Period 2 Day 11 Morning: predose, 1h, 2h, 3h, 6h similar “postdose” ; Evening: 0.5h “postdose”
 
Treatment Period 3a Day 22: Morning: predose, 1h, 2h, 3h, 6h similar “postdose” ; Evening: 0.5h “postdose”
 
Treatment Period 3b Day 25: Morning: predose, 1h,2h,3h, 6h similar “postdose” ; Evening: 0.5h “postdose”
 
Treatment Period 3c Day 33: Morning: predose, 1h,2h,3h, 6h similar “postdose” ; Evening: 0.5h “postdose”
 
Otherwise baseline = day -1 predose

ECG=electrocardiogram; SFU=Safety Follow-Up.

If a measurement is repeated at Baseline or a given treatment period and is obtained prior to dosing in that period, then the last available measurement will be used as the Baseline value.

12-lead ECG will be measured in triplicate with a 1-minute interval between replicates. Mean of the last three measurements predose will be taken as the baseline; if less than three replicates are available predose, the mean of the available replicates (predose) will be taken as the baseline.

Time matched predose values are defined as the Baseline value (see Table 3-1).

The change from Baseline to any subsequent post-Baseline visit will be calculated as the simple difference between that post-Baseline visit’s value and the Baseline value, as below:

$$Post - Baseline Visit Value - Baseline Visit Value$$

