3.6 Treatment assignment and treatment group

All subjects will complete the identical fixed-sequence multiple-dose treatments. Listings will be presented by subject and treatment period (Screening, Treatment Periods 1, 2, 3a, 3b and 3c, and SFU). Summaries will be presented by treatment (PSL, erythromycin, PSL + erythromycin and SFU), unless stated otherwise.

- PSL Treatment Period 1 and 2 (pooled data)
- Erythromycin Treatment Period 3a and 3c (pooled data)

- PSL + Erythromycin Treatment Period 3b
- SFU

Adverse events summaries will be presented by treatment within treatment periods as follows:

- Period 1 and 2: PSL
- Period 3a: Erythromycin (pre-PSL)
- Period 3b: PSL + Erythromycin
- Period 3c: Erythromycin (post-PSL)
- SFU

PK summaries will be presented as follows:

- PSL: Period 1
- PSL: Period 2
- PSL + Erythromycin: Period 3b

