10.4.2 Electrocardiograms

12-lead ECG will be recorded 3 times at each time point. The individual mean at each time point will be calculated as raw parameters for descriptive analysis. The individual mean and change from baseline (time-matched Baseline day of each treatment period, when applicable) will be summarized using descriptive statistics by treatment period at each time point.

All standard 12-lead ECG recordings will be taken in triplicate with the subject resting in the supine position for at least 10 minutes. The following ECG parameters will be reported:

- PR interval
- QT interval
- QRS interval
- RR interval
- QTc interval (QT corrected for heart rate using Fridericia’s formula [QTcF])
- Heart rate

If available in the database, the QT corrected for heart rate using Bazett’s formula (QTcB) will also be included in the listings and tabulations.

The individual measurements and the mean of the triplicate measurements will be reported in the by-subject listings. The listing will also include the change from Baseline (time-matched Baseline day of each treatment period, when applicable), based on the mean of the triplicate measurements at each timepoint, and will be presented by treatment period and timepoint.

Measured values and changes from time-matched Baseline will be summarized by treatment period and at each timepoint and by ECG variable (based on the mean of the triplicate values at each timepoint). The summaries will include the 2-sided 95% CIs. Mean change from time-matched Baseline in QTcF will be summarized and plotted over time. Figures will be presented with all treatment periods overlaid on the same plot.

The following cut-points in QTcF (observed data and change from time-matched Baseline), based on the mean of the triplicate data, will be summarized categorically (number and percentage of subjects) by treatment period at each timepoint.

For observed data:

- <450msec
- ≥450 to <480msec
- ≥480 to <500msec
- ≥500msec

Absolute change from Baseline in QTcF:

- <30msec
- ≥30 to <60msec
- ≥60 msec

All ECG findings for the individual triplicate measurements will be listed separately.

Any incomplete triplicate measurements at a given timepoint will be handled as described in [Section 4.2.3](#).

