13 APPENDICES

13.1 Breakdown of treatment periods reported into the TFLs by study assessment data

Table 13.1: Breakdown of treatment periods reported into the TFLs by study assessment data

Treatment	PSL		PSL	Erythromycin pre	PSL + Erythromycin	Erythromycin post	EOS/SFU	All subjects
	Period 1	Period 2	Period 1 + 2	Period 3a	Period 3b	Period 3c		
Subject disposition	X	X		X	X	X	X	
Protocol deviations	X	X		X	X	X	X	
Demographics								X
Medical history								X
Lifestyle								X
Prior/concomitant medications								X
Adverse Events			X	X	X	X	X	
Laboratory tests	X	X			X	X	X	
Other safety continuous measurements (vital signs, ECG)	X	X		X	X	X	X	
Safety categorical results (laboratory shift tables, PDILI)	X	X			X	X		
PK plasma and urine for PSL and metabolites	X	X			X			

ECG=electrocardiogram; EOS=end of study; PK=pharmacokinetic; PSL=Padsevonil; SFU=Safety Follow-up.

Note: Period refers to the treatment period.

14 **AMENDMENT(S) TO THE STATISTICAL ANALYSIS PLAN**

Not Applicable

This document cannot be used to support any marketing authorization application and any extensions or variations thereof.

REDACTED COPY

STATISTICAL ANALYSIS PLAN SIGNATURE PAGE

This document has been reviewed and approved per the Review and Approval of Clinical Documents Standard Operating Procedures. Signatures indicate that the final version of the SAP or amended SAP is released for execution.

This document cannot be used to support any marketing authorization application and any extensions or variations thereof.

REDACTED COPY

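### The SAP averages Periods 3a and 3c for continuous safety data against its own Table 13.1, and for ECG change from baseline the average mixes a Day 22 and a Day 33 baseline and cannot be interpreted

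*SAP*

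**What the plan says.** SAP Section 10 sets the default for safety summaries. Periods 1 and 2 form one group, and so do 3a and 3c: "Period 3a and Period 3c pooled and EOS/SFU) as detailed in" Table 13.1. For continuous data it adds: "Summaries for continuous variables by timepoint will be based on the averaged value across the pooled periods". Categorical results are kept by actual period.

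SAP Section 3.6 repeats the grouping: "Erythromycin Treatment Period 3a and 3c (pooled data"). The same section keeps 3a and 3c apart for adverse events, as erythromycin before and after PSL.

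The row of Table 13.1 for "Other safety continuous measurements (vital signs, ECG") has a separate mark under Periods 1, 2, 3a, 3b, 3c and EOS/SFU. The combined Period 1 + 2 column is blank in that row, and the table has no combined 3a+3c column.

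SAP Section 10.4.2 says: "Measured values and changes from time-matched Baseline will be summarized by treatment period and at each timepoint and by ECG variable".

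The ECG baselines are in SAP Section 3.3, Table 3-1. For 3a: "Treatment Period 3a Day 22: Morning: predose, 1h, 2h, 3h, 6h similar". For 3c: "Treatment Period 3c Day 33: Morning: predose". Period 3b uses Day 25.

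**The concern.** Two things look wrong.

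First, Section 10 gives one instruction and names as its detail a table that shows another. A programmer could deliver pooled or separate tables and claim compliance with either.

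Second, if the averaging is carried out, the ECG change for erythromycin alone combines two different contrasts. The 3a part compares erythromycin with no study drug. The 3c part compares erythromycin after PSL with a day on both drugs. Their average estimates neither. Change in 12-lead ECG is a named safety variable, and mean QTcF change from time-matched baseline is to be tabulated and plotted. An erythromycin effect on QTcF could therefore be understated in the column meant to show it.

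**Working it through.** The plan gives no figure to reproduce, so the check compares the texts and then works through the ECG algebra.

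**1. Which periods are combined?**
- SAP Sections 10 and 3.6: 1 with 2, and 3a with 3c; continuous values averaged.
- SAP Table 13.1, vital signs and ECG row: all five periods separate.
- SAP Sections 10.4.1 and 10.4.2 and Protocol Section 12.3.2: by treatment period. This does not settle the matter, because Section 10 uses the same phrase for its pooled groups.
- Protocol Section 12.1.2: safety by treatment, including erythromycin alone.

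**2. What is given on each ECG baseline day?**
- Day 22 (for 3a): no study drug (Protocol Section 7.8.3). The last PSL dose was on the morning of Day 16, 144 h earlier.
- Day 25 (for 3b): erythromycin only.
- Day 33 (for 3c): PSL in the morning plus erythromycin twice daily (Protocol Section 5.2.2.2.2).
- Protocol Section 10.3.3 lists ECG run-in days as Days -1, 11, 22 and 25. Day 33 is not among them.

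**3. Algebra.** Let E be the erythromycin effect (taken as steady), P the added PSL effect on Day 33, and r the share of P remaining in 3c, all relative to no drug.
- 3a change from Day 22 = E
- 3c change from Day 33 = (E + rP) − (E + P) = −(1 − r)P
- Equal-weight average = [E − (1 − r)P]/2
- Weighted by dosing days (3 in 3a, 4 in 3c) = [3E − 4(1 − r)P]/7

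**4. Numbers.** E = 10 ms is an assumption for illustration; the documents give no effect sizes.

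| P (ms) | r | 3a | 3c | Equal average | 3:4 average |
|---|---|---|---|---|---|
| −5 | 0 | 10 | 5 | 7.5 | 7.1 |
| 0 | 0 | 10 | 0 | 5.0 | 4.3 |
| 5 | 0 | 10 | −5 | 2.5 | 1.4 |
| 5 | 0.25 | 10 | −3.75 | 3.1 | 2.1 |
| 10 | 0 | 10 | −10 | 0.0 | −1.4 |

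With P = 0 the equal-weight average is E/2 whatever E is. It equals E only when (1 − r)P = −E.

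**5. Residual PSL in 3c.** The last PSL dose is on the morning of Day 33, there is no wash-out before 3c (SAP Section 10.2), and sampling continues at "24h, 36h, 48h, 60h, 72h, 96h, and 120h post last dose of PSL during Treatment Period 3b". No half-life is given, so it is assumed over a range. The fraction left is 0.5^(t/half-life).
- Day 34 morning (24 h): 1.6%, 6.2%, 12.5%, 25% and 50% for half-lives of 4, 6, 8, 12 and 24 h.
- Day 37 morning (96 h): at most 0.4% for half-lives up to 12 h, and 6.2% for 24 h.

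**6. Which data are affected?**
- *Vital signs:* one baseline, predose Day 23, serves all of Period 3 (Table 3-1). The Table 13.1 conflict applies; the baseline problem does not.
- *Laboratory tests:* Period 3 samples are on Days 26, 30, 33 and 37 (Protocol Table 5-1, laboratory footnote). None falls in 3a, so there is nothing to average with 3c.
- *Pairing:* within-day ECG times match in 3a and 3c, but with 3 and 4 dosing days the SAP does not say how days are aligned or weighted.

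**7. With Day 22 as baseline for both periods.** 3a change = E, 3c change = E + rP, and their average = E + rP/2. For E = 10 and P = 5, the average is 10 ms if r = 0, and (10 + 11.25)/2 = 10.6 ms if r = 0.25.

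**The case against.** The best defence is that the averaged value may never be produced. Section 10 allows other statements to override its default, and Table 13.1, Section 10.4 and Protocol Section 12.3.2 can all be read as requiring separate periods. That is a fair reason to call the first defect an inconsistency rather than a settled choice. It does not remove it: Section 10 presents the conflicting table as its own detail, and no order of precedence is given. Nor does dropping the pooling cure the Day 33 baseline. The 3c column alone would still estimate −(1 − r)P, which is not an erythromycin effect. The QTcF change categories in 3c, although unpooled, would carry the same baseline.

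The pooling also has a basis in Protocol Section 12.1.2, which asks for an erythromycin-alone summary. That stands. It means such a summary should be computed properly, not that the grouping must be struck out.

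A reader might infer more than the documents support:
- *That 3c days contain PSL.* No PSL is dosed in 3c. Carry-over is possible early in the period, but no half-life or concentration is given, and sampling to 120 h is a plan, not evidence that PSL is present.
- *That the pooled column spoils the comparison for 3b in the secondary safety objective.* That objective sets PSL with erythromycin against PSL alone. Its variable is adverse events, which are reported with 3a and 3c apart.
- *That all continuous safety changes are distorted.* Only ECG change has the baseline problem.
- *That Day 25 is a wrong baseline for 3b.* It is planned in the protocol and isolates the PSL increment.

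Listings by period and timepoint also remain available to a careful reader.

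**Conclusion.** Two defects hold. Sections 10 and 3.6 contradict the vital signs and ECG row of Table 13.1, for the 1+2 pooling as well as 3a+3c. And if the text of Section 10 is followed, the averaged 3a+3c ECG change is [E − (1 − r)P]/2, which has no clear meaning as an erythromycin effect.

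The halving when there is no PSL effect follows from the baseline definitions, given equal weights and a steady erythromycin effect. The millisecond figures are illustrative, and the direction of the error depends on the sign and size of P. A PSL effect opposite in sign to E would offset some of the loss.

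The outputs concerned are descriptive, and neither the primary PK analysis nor the adverse event tables are touched. This should be corrected before the table shells are fixed.

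**What to change.** - Make SAP Sections 10 and 3.6 agree with Table 13.1: report vital signs and ECG separately for Periods 1, 2, 3a, 3b and 3c, with 3a and 3c labelled erythromycin pre-PSL and post-PSL.
- In Table 3-1, replace Day 33 with the time-matched Day 22 as the ECG baseline for 3c, as already used for 3a.
- Keep Day 25 as the 3b baseline, which under a steady erythromycin effect gives P. Add change from Day 22 as an extra 3b column, which gives E + P.
- If a pooled erythromycin-alone summary is kept to meet Protocol Section 12.1.2, compute its ECG change from Day 22 in both periods, state how days are aligned and weighted, and show it beside the separate columns.

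The cost is SAP wording, revised table shells and a few more columns. The Day 22 ECGs are already scheduled at the matching times, so no new data are needed.
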